Processes of Care Measures (Aim 2): At the conclusion of each patient's participation, we will extract medical record data on treatment received. This will include data in the year prior to treatment and the year during treatment on number of urine drug tests administered as part of clinical care and queries to state prescription drug monitoring programs. Results from UDTs administered as part of clinical will be extracted from VA laboratory data. For PDMP data, clinicians must provide documentation in the medical record when they check PDMP data; research staff will review medical record data of enrolled participants to evaluate incidence and frequency of PDMP checks. For patients with documented prescription opioid abuse, research staff will evaluate any potential changes in care that occurred following detection of prescription opioid abuse, including referrals to the substance abuse treatment program, mental health clinic, or specialty pain service; follow-up monitoring; and treatment changes (such as change in opioid or dose, cessation of opioids, etc.).

➤ Although the research team will monitor UDTs administered in clinical practice, these data will not be used as outcome to reflect prescription opioid abuse. UDTs will also be administered by the research team to all participants at all three research visits. These UDTs will be ordered under a unique study identification number. Patient identifying information will never be attached to or associated with these research UDT sample.

Measures of the Clinician-Patient Relationship (Aim 2): Trust in one's clinician will be examined with the Trust in Physician Scale, an 11-item self-report measure assessing interpersonal trust in patient-clinician relationships.⁸⁴ This has been used extensively as an outcome measure in prior studies examining patient-centered care and shared decision-making, and has evidenced strong psychometric properties.⁸⁵ The Participatory Decision Making Style is a brief self-report measure designed to assess level of patient involvement in medical decision making.⁸⁶ Both of these measures have been shown to be responsive to interventions directed towards by PCPs and allied health professionals.⁸⁷ The Positive Regard Scale is a recently-developed 5-item self-report measure that evaluates patients' perceptions of their relationship with their primary care provider.

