observations on different patients of the same PCP and for repeat observations on the same patient. Transformations of the outcome will be applied to meet distributional assumptions. In linear mixed models, we will include baseline measures of patient age, sex, depressive symptoms, history of SUD, and pain severity as covariates. We will also adjust for baseline COMM score and the stratification variables: PCP training type (MD/DO vs NP or PA) and proportion of clinician panel prescribed opioids (high vs low). In addition to testing formal hypotheses, we will report 95% confidence intervals for the differences in mean outcomes between groups at 6 and 12 months. For comparing the percentages classified as abusing opioids at any time during follow-up (combining information from 6 and 12 months) based on SCID and UDT, we will use generalized-linear mixed models (or GEE as needed) to incorporate correlation between patients of the same PCP. We will adjust for baseline measures of the outcome along with the covariates listed above. We will report group comparisons on all three primary outcomes (COMM, SCID, and UDT). Assuming 15% of the sample has current SUD (consistent with other research), we will not conduct interaction analyses, but will present descriptive information for each outcome (COMM, SCID, UDT) on treatment outcomes by SUD status.

Data on opioid-related adverse events will be obtained from the medical record and participant self-report. We will collect data on opioid overdoses, falls, motor vehicle accidents, and ER visits related to pain. Descriptive information on opioid-related events will be provided for each group (numbers and percentages of participants with each event). Because the number of adverse events is expected to be small, we will use Fisher's Exact test to compare adverse event percentages between groups. We will compare both percentages for each individual type of event as well as percentages of individuals experiencing any adverse event between groups.

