Clinicians will also be queried about perceived barriers and potential effectiveness of screening for prescription opioid abuse. With 32 pairs of clinicians and intra-class correlations of 0 to 0.1, we would have 80% power to detect differences of 0.50 to 0.53 SDs in mean summary scores between intervention groups.

Analyses for Aim 2: We will use GEE methods to compare between intervention groups the average numbers of clinical care documentations, UDT's, and queries to state prescription drug monitoring programs while adjusting for the baseline covariates (age, gender, depressive symptoms, history of SUD, and pain intensity) and the stratification variables. For patient level data, the approach for analysis of Aim 2 outcomes will be the same as that for Aim 1, using mixed models and/or GEE for comparisons, while adjusting for baseline covariates (age, sex, depressive symptoms, history of SUD, and pain severity), baseline measure of the outcome, and stratification variables (training type, proportion of panel prescribed opioids). Analyses will be conducted for scores on the Trust in Physician scale and Participatory Decision Making Style.

For clinician and PACT nurse data on barriers to use of UDTs, we will report descriptive information for each of the 10 questions. For each group and question, we will report the percentage of clinicians with scores at each of the five levels at baseline and follow-up, as well as the corresponding descriptive change information in follow-up scores. We will report the mean (and SD, min, max) of change for each question. We will obtain an overall survey score, by averaging the 10 question scores for each clinician and report the mean (and SD, min, max) survey score for each group at baseline and follow-up, along with the mean change (and SD, min, max) in survey score. We will use linear mixed models on the change scores to compare groups, while adjusting for clinician age, clinician training type, sex, panel size, summary survey score at baseline, and stratification variables. We will include a random pair effect to allow for correlation between the PCP and PACT nurse within each pair. P-values and 95% confidence intervals for the differences between groups in change scores will be provided. Similar analyses will be conducted for examining survey data on clinician satisfaction with ISOT.

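### The covariate list for the Aim 2 UDT and PDMP count models omits the patient's prior-year count, and it is unclear whether the adjacent list that adds the baseline outcome applies

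*Combined protocol and SAP*

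**What the plan says.** All references are to the combined protocol and SAP.

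- **Analyses for Aim 2, first sentence.** GEE will compare "the average numbers of clinical care documentations, UDT's, and queries to state prescription drug monitoring programs" between groups, "while adjusting for the baseline covariates (age, gender, depressive symptoms, history of SUD, and pain intensity) and the stratification variables". No baseline count is named.
- **Analyses for Aim 2, second sentence.** "For patient level data, the approach for analysis of Aim 2 outcomes will be the same as that for Aim 1". It goes on to list mixed models and/or GEE, the same patient covariates, and "baseline measure of the outcome, and stratification variables (training type, proportion of panel prescribed opioids".
- **Analyses for Aim 2, third sentence.** "Analyses will be conducted for scores on the Trust in Physician scale and Participatory Decision Making Style". It names no process count.
- **Processes of Care Measures (Aim 2).** On the medical record extraction: "This will include data in the year prior to treatment and the year during treatment on number of urine drug tests administered". State PDMP queries are named in the same sentence.
- **Analyses for Aim 1.** For the binary SCID and research UDT outcomes: "We will adjust for baseline measures of the outcome along with the covariates listed above". The COMM model adjusts for baseline COMM.
- **Elsewhere.** The clinician barrier survey model includes the baseline survey score, and the Aim 3 models include the baseline score.

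**The concern.** How often a patient is tested is likely to persist from one year to the next, both because PCPs differ in habit and because patients differ in perceived risk. If so, the prior-year count is probably the best single predictor of the follow-up count. The trial plans to collect it, but the sentence that specifies the count model does not use it.

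Two things are at stake. The first is precision. Randomisation is by PCP, with 28 to 32 per arm, stratified by training type and by the proportion of the panel on opioids but not by testing practice. A chance difference in prior testing between 56-64 PCPs would therefore enter the unadjusted estimate.

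The second is specification. Two analysts could reasonably fit different models to Aim 2 Hypothesis 1, one with the baseline count and one without, and each could point to a sentence in the plan.

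**Working it through.** **1. Is the count left out?** The two lists in Analyses for Aim 2 differ in one substantive item, the baseline value of the outcome.

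- *For omission:* the count outcomes have their own complete list. That list would be redundant if the second one governed them. The sentence after the second list names only the two relationship scales.
- *For inclusion:* UDT and PDMP counts are patient-level Aim 2 outcomes, and the second sentence itself names no scale.

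Omission is the more natural reading but is not certain.

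**2. The plan's own UDT figure.** Table 2 gives the UDT percentage detectable against 40% in control at 80% power and alpha 0.05. With m patients per PCP and k PCPs per arm, effective n per arm = mk / (1 + (m − 1) × ICC). For 32 PCPs, 5 patients and ICC 0.02 this is 160 / 1.08 = 148.1. The pooled two-sided two-proportion formula then gives 56.2%, against 56% stated. All 16 cells reproduce after rounding. No power figure is given for counts.

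**3. Value of the covariate for UDT.** The documents give no correlation for these counts; the 0.5 used for the Aim 3 change SDs concerns other measures. Let r be the assumed correlation between prior-year and follow-up values that remains after the other covariates. The residual variance is multiplied by 1 − r², the standard error (SE) by √(1 − r²), and the effective sample size by 1 / (1 − r²).

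| Assumed r | 1 − r² | SE reduction | Effective n | Detectable UDT % (32 × 5, ICC 0.02) |
|---|---|---|---|---|
| 0 | 1.00 | 0 | 0 | 56.2 |
| 0.1 | 0.99 | 0.5% | +1% | 56.1 |
| 0.3 | 0.91 | 4.6% | +10% | 55.5 |
| 0.5 | 0.75 | 13.4% | +33% | 54.0 |
| 0.6 | 0.64 | 20.0% | +56% | 53.0 |

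This is a linear-model result, so it was checked with a simulated Poisson GEE clustered on PCP, with and without log(1 + prior-year count), at 300 runs per scenario. Means were set for roughly 26% with any baseline test and 40% with any follow-up test in control. The Poisson family is an assumption, since the plan names none.

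| Scenario | Count correlation | Model SE without → with | Reduction |
|---|---|---|---|
| Weak persistence | 0.16 | 0.158 → 0.153 | 3% |
| Moderate | 0.37 | 0.187 → 0.168 | 11% (10.5% before rounding) |
| Strong | 0.52 | 0.218 → 0.179 | 18% |
| Moderate, ISOT adds tests mainly for untested patients | 0.33 | 0.154 → 0.144 | 7% |
| Strong, same | 0.47 | 0.178 → 0.154 | 14% |

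The empirical spread of the estimates fell by a similar amount (3%, 11% and 15% in the first three rows). The mean log rate ratio differed by no more than 0.01 with and without the covariate, so in these scenarios the covariate changes precision and not the answer. The last two rows are relevant because, under System Assessment and Intervention, the nurse care manager's UDT and PDMP prompts depend on whether the patient had a past-year test or check.

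**4. Value for PDMP.** The Aim 2 power text says 3-5% of patients currently receive a query. For an any/none indicator with prevalence p before and q after (p < q), the largest possible R² is p(1 − q) / [q(1 − p)]. Follow-up rates of 40% to 80% are assumed for ISOT.

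- p = 0.05, q = 0.40: 0.030 / 0.380 = 0.079, so the SE falls by at most 4.0%.
- p = 0.03, q = 0.40: 0.018 / 0.388 = 0.046, at most 2.3%.
- p = 0.05, q = 0.80: 0.010 / 0.760 = 0.013, at most 0.7%.

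The ceiling holds at those follow-up rates. In a control arm still near 3-5% the same formula barely constrains R² (0.59 for p = 0.03, q = 0.05), so it says nothing useful there.

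**5. Is power at stake?** Without the covariate and at ICC 0.02, power over the four planned configurations is 0.83 to 0.94 for 40% versus 60% with any UDT, and at least 0.99 for 40% versus 70%. The plan expects differences well beyond its detectable range.

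**The case against.** The strongest reply is that the plan already does this. The patient-level sentence extends the Aim 1 approach to Aim 2 outcomes and includes the baseline outcome. The natural contrast to patient-level data is the clinician and nurse survey in the next paragraph, not the process counts. This stands to the extent that omission cannot be called certain. It does not remove the problem, because the plan never says that the second list supersedes the first for counts.

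Four stronger readings are tempting and should be resisted.

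- **The plan definitely discards the prior-year data.** A reader might infer this from the first list alone. The following sentence leaves room for the opposite.
- **Aim 2 is underpowered or biased without the covariate.** It is neither on this account. Power is ample at the expected effects. Leaving out a baseline covariate does not in itself bias a randomised comparison, and the interval already allows for chance imbalance, only less efficiently.
- **The gain is large for every process measure.** The upper figures need a residual correlation near 0.6, which the documents do not supply. A raw year-to-year correlation may overstate it, because SUD history, pain, depressive symptoms and panel opioid proportion are already in the model. The PDMP gain is probably small.
- **The change is free.** The extraction covers the year before treatment, whereas PCPs are randomised before patients are recruited. A patient's prior year could therefore overlap the PCP's workshop or contact with the nurse care manager. Adjusting for testing already altered by the intervention could absorb part of the effect, so the window needs care. In addition, prior-year extraction is stated for UDTs and PDMP queries but not for clinical care documentations, the third outcome in the same sentence.

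**Conclusion.** The point holds as a worthwhile correction to the specification. It is certain that the two covariate lists differ on the baseline outcome, and that prior-year UDT and PDMP counts are to be extracted. It is likely, but not certain, that the count model as written leaves them out. If so, this model departs from the plan's own practice in its COMM, SCID and research UDT, relationship-scale, clinician-survey and Aim 3 models.

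For UDT the plausible gain is an SE about 0.5% to 20% smaller, on an assumed residual r of 0.1 to 0.6. The simulated Poisson GEE gave 3-18% at count correlations of about 0.16-0.52. For PDMP the gain is at most about 4%, given 3-5% queried beforehand and assumed follow-up rates of 40-80%. What is gained is a tighter interval, less exposure to chance imbalance, and a single unambiguous model. No conclusion about the feasibility of Aim 2 follows.

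**What to change.** In Analyses for Aim 2, add to the count GEE sentence that the models for UDT counts and for PDMP query counts also adjust for the patient's prior-year count of the same measure, or an any/none indicator, as extracted under Processes of Care Measures. Choose the form in advance.

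Define the 12-month window so that it ends before the PCP's exposure to the study intervention, and use that definition in the extraction section too. Limit the addition to UDT and PDMP. For clinical care documentations, keep the existing list unless a prior-year value is shown to be collected. State also that the patient-level sentence that follows governs the relationship scales, so that each outcome has one covariate list.

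The cost is a sentence or two of text, one covariate per model and, for some patients, possibly an earlier extraction window.
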